## List of abbreviations

AE	Adverse Event
ARR	Annualized Relapse Rate
ATC	Anatomical Therapeutic Chemical
BDNF	Brain-Derived Neurotrophic Factor
BMI	Body Mass Index
[REDACTED]	[REDACTED]
CD19	Cluster of Differentiation 19
CDBL	Clinical Database Lock
[REDACTED]	[REDACTED]
CI	Confidence Interval
CNS	Central Nervous System
CRO	Contract Research Organization
[REDACTED]	[REDACTED]
CSP	Clinical Study Protocol
CSR	Clinical Study Report
C-SSRS	Columbia-Suicide Severity Rating Scale
[REDACTED]	[REDACTED]
DMT	Disease Modifying Therapy
EDSS	Expanded Disability Status Scale
EOS	End of Study
FAS	Full Analysis Set
Gd	Gadolinium
[REDACTED]	[REDACTED]
HCAS	Healthy Control Analysis Set
IA	Interim Analysis
[REDACTED]	[REDACTED]
[REDACTED]	[REDACTED]
MCP1	Monocyte Chemoattractant Protein
MedDRA	Medical Dictionary for Drug Regulatory Activities
mFAS	Modified Full Analysis Set
MPR	Medication Possession Ratio
[REDACTED]	[REDACTED]
[REDACTED]	[REDACTED]
MS	Multiple Sclerosis
NBV	Normalized Brian Volume
NEDA	No Evidence of Disease Activity

NeuroQOL™	Quality of Life in Neurological Disorders
NfL	Neurofilament Light
██████	██████████
NRI	Non-Response Imputation
PBVC	Percentage Brain Volume Change
PD	Pharmacodynamic
PDC	Proportion of Days Covered
PDDS	Patient Determined Disease Steps
PK	Pharmacokinetic
PRO	Patient Reported Outcome
PT	Preferred Term
RRMS	Relapsing-Remitting Multiple Sclerosis
SAE	Serious Adverse Event
SAF	Safety Analysis Set
SAP	Statistical Analysis Plan
██████	████████████████████
SOC	System Organ Class
██████	██████████
TFL	Tables, Figures and Listings
UBC	United BioSource LLC
USPI	United States Prescribing Information
WHO	World Health Organization

## 1 Introduction

The purpose of this Statistical Analysis Plan (SAP) is to describe the data analysis and statistical methods planned in Section 12 of the Clinical Study Protocol (CSP) version 03 (dated 14-Sep-2023) for the clinical trial COMB157GUS10 and any additional analyses, specifications or deviations from this planned protocol before clinical database lock (CDBL).

This SAP will be used to draft the Clinical Study Report (CSR) Section 9.7: Statistical methods. It will also be used to draft the statistical methods section of the Interim Analysis Report.

### 1.1 Study design

This study is an open-label, multi-center, prospective eighteen-month study in a minimum of 118 multiple sclerosis (MS) patients with early relapsing-remitting MS (RRMS) (defined as within 6 months of diagnosis of clinically definite RRMS) and who are disease modifying therapy (DMT) treatment naïve. RRMS patients will be benchmarked against age- and sex-matched healthy controls (n=50) for select secondary [REDACTED] outcomes.

The study consists of 3 main periods/phases as outlined below. In addition, a safety follow-up period applies to participants who meet specific criteria as described below.

#### Screening period

Participants will enter a screening period of up to 4 weeks to assess eligibility requirements.

#### Open-label treatment phase

Eligible participants with RRMS will receive ofatumumab 20 mg subcutaneous doses during the open-label treatment phase at Baseline/Week 0 (Day 1), followed by Week 1 (Day 7), Week 2 (Day 14) and then every month thereafter, beginning at Week 4 (Month 1) until Month 18 (see [Figure 1](#)). Ofatumumab will be administered according to the United States Prescribing Information (USPI). RRMS patients must remain on ofatumumab monotherapy to remain in the trial, with no DMT switching or combination DMT therapy allowed.

Healthy control participants will not be given a therapy.

#### Optional open-label extension period

Additional efficacy and safety assessments will be evaluated during the optional open-label extension period to further elucidate the long-term clinical and radiological effects of ofatumumab (see [Figure 1](#)). Of note, magnetic resonance imaging (MRI) data will be re-baselined at Month 6 to account for treatment-related pseudo atrophy.

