The proposed study would provide rigorous clinical, MRI, digital and biomarker data demonstrating the effect of ofatumumab in a naïve RRMS population at first diagnosis and would provide the first data relative to healthy controls, identified data gaps in the US. The very early MS young adult population in this study will consist of treatment naïve RRMS patients that are within 6 months of diagnosis at the time of study entry. Detailed data will be collected within the first month to document a rapid response to therapy. Further, a HC group will be used to analyze select endpoints vs ofatumumab (e.g., brain atrophy) with the strategy of showing normalization of brain structural/functional changes. This would also highlight the need for high efficacy therapy very early in the course of the disease as the extension data of up to 30 months would potentially show stabilization long term.

2 Objectives, endpoints and estimands

Table 2-1 Objectives and related endpoints

[figure not shown]
Objective(s)	Endpoint(s)

Primary Objective(s)
 
 The primary objective is to explore the impact of ofatumumab (OMB) on the ability to achieve No Evidence of Disease Activity (NEDA-3) status in treatment-naïve, very early RRMS patients over an 18 month, open-label study period after a re-baseline of MRI at 6 months 	
Endpoint(s) for primary objective(s)
 
 NEDA-3 (Relapse-free, 3-month clinical disability progression-free, MRI activity-free) in Months 6 to 18 (yes/no)

Secondary Objective(s)
 
Evaluate the effect of ofatumumab on various clinical (NEDA, disability, relapse) metrics at 18 months
	
Endpoint(s) for secondary objective(s)
 
Baseline and months 6, 12, 18, 30 (T1 Gd)

 Evaluate the effect of ofatumumab on conventional MRI metrics, with MRIs at 	

- Number of relapses
- 3-month Disability Worsening-free (yes/no)
- NEDA clinical in Months 6 to 18 (yes/no)
- NEDA radiological in Months 6 to 18 (yes/no)
- Change from Baseline in Conventional MRI metrics
(Gd+ lesion number, new Gd+ lesion number, Gd+ lesion volume, T2 lesion

Objective(s)	Endpoint(s)
@ Baseline, month 6, 18 and T1/T2 @ every timepoint)	number (Baseline), New/enlarging T2 lesion number (post-Baseline), T2 lesion volume, new unenhancing T1 lesion number, T1 unenhancing lesion volume)

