2.2 Secondary estimands

Not applicable.

3 Study design

This study is an open-label, multi-center, prospective eighteen-month study in a minimum of

118 MS patients with early RRMS (defined as within 6 months of diagnosis of clinically

definite RRMS) and who are disease modifying therapy (DMT) treatment naïve. RRMS patients will be benchmarked against age- and sex-matched healthy controls (n=50) for select secondary [REDACTED]. A screening period of 4 weeks will be used to assess eligibility and the assessment to address the primary objective will be performed at the end of the maintenance period (Month 18). There will be one interim analysis after the last participant completes his/her Month 18 (primary analysis time point) visit. Participants who complete the treatment period or who prematurely discontinue study drug and the study, and do not continue on any MS DMT, will undergo a safety evaluation 100 days following last dose of study treatment (captured only in source documents and only for ofatumumab treated participants), and will be discharged from the study if they choose to not be included in the optional extension portion of the trial for an additional 12 months (up to 30 months total in trial). Healthy control participants will not have a safety evaluation post end of study. Additional efficacy and safety assessments will be evaluated during the optional open-label extension to further elucidate the long-term clinical and radiological effects of ofatumumab (Figure 3-1). Of note, MRI data will be re-baselined at month 6 to account for treatment-related pseudo atrophy.

[figure not shown]
Eligible participants with RRMS will receive ofatumumab 20mg subcutaneous doses at Baseline/Week 0 (Day 1), followed by Week 1 (Day 7), Week 2 (Day 14) and then every month thereafter, beginning at Week 4 (Month 1) until Month 18 (see Figure 3-1). Additional efficacy and safety assessments will be evaluated up to 30 months, necessitating ofatumumab monotherapy over the course of up to 30 months. Ofatumumab will be administered according to the United States Prescribing Information (USPI). RRMS patients must remain on ofatumumab monotherapy to remain in the trial, with no DMT switching or combination DMT therapy allowed. Healthy controls will not be given a therapy.

Assessments will be performed per the assessment schedule found in Table 8-1.

Figure 3-1 Study design

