O = Ofatumumab participant

H = Healthy Control

X = assessment to be recorded in the clinical database or received electronically from a vendor

S = assessment to be recorded in the source documentation only

■ [Redacted]

² Relapse assessment will be performed in scheduled, as well as unscheduled visits as deemed necessary by the Investigator or designee. Assessment can be done on site or via remote procedures

³ Urine β-hCG will be conducted monthly, at home, as well as, at defined clinical visits (scheduled and unscheduled)

[Redacted]

⁴ Assessment during an unscheduled visit will be performed as deemed necessary by the investigator, **except** for vital signs and evaluation of AE, which are mandatory at each visit

⁶ Participants are not required to come to the study site. Remote contact with participants, by site staff around the time of at-home, self-administration of ofatumumab should query about any new or worsening symptoms warranting an unscheduled visit, MS relapse, compliance with study treatment [REDACTED], adverse events, and compliance with contraception requirements (when applicable). The method of contact can be via telephone, email, video conference or text message depending on the preference of each participant

⁷ For the first injection, vital signs should be obtained 30-60 minutes before sc injection and again approximately 60 minutes post-injection

⁸ All lab assessments should be taken prior to dosing at the Day 1 visit. For any later biomarker visits, if the visit coincides with the day the monthly injection is scheduled, the subject should not take the injection in the morning before coming to the site so that the biomarker sample can be drawn before the injection

⁹ Labs must be drawn to allow adequate time for results to be obtained before first study drug administration to ensure participant's eligibility

¹⁰ Urine dipstick: If abnormal send full urinalysis to central laboratory

¹² Data for safety follow-up visit will be captured in source documentation only. Safety follow-up participants are not required to come to study site and lab assessments should be done locally

¹³ Only for participants continuing onto the 12-month open-label extension period

¹⁴ Gadolinium will not be given to healthy controls and gadolinium enhanced T1 MRI imaging will not be conducted in healthy controls

¹⁵ The C-SSRS must be administered at either screening or baseline, then at every on-site visit thereafter until End of Study (EOS)

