**Table 1 Study objectives and endpoints**

Objective(s)	Endpoint(s)

Primary Objective(s)
 
 
The primary objective is to explore the impact of ofatumumab on the ability to achieve No Evidence of Disease Activity (NEDA-3) status in treatment-naïve, very early RRMS participants over an 18 month, open-label study period after a re-baseline of MRI at 6 months
 
	
Endpoint(s) for primary objective(s)
 
 
NEDA-3 (relapse-free, 3-month clinical disability progression-free, MRI activity-free) in Months 6 to 18 (yes/no)
 

Secondary Objective(s)
 
 
Evaluate the effect of ofatumumab on various clinical (NEDA, disability, relapse) metrics at 18 months
 
Evaluate the effect of ofatumumab on conventional MRI metrics, with MRIs at Baseline and Months 6, 12, 18, 30 (T1 gadolinium (Gd) @ Baseline, Month 6, 18 and T1/T2 @ every timepoint)
 
Evaluate the effect of ofatumumab on patient reported outcomes (PROs) (Quality of Life in Neurological Disorders [NeuroQOLTM], Patient Determined Disease Steps [PDDS])
 
Evaluate the effect of ofatumumab vs healthy controls on 1) whole brain and regional atrophy measured at Month 18/30 after re-baseline at 6 months; and 2) regional atrophy measured 18/30 months from Baseline
 
Evaluate the safety and tolerability of ofatumumab
 
	
Endpoint(s) for secondary objective(s)
 
 
Number of confirmed relapses in Months 6 to 18
 
3-month disability worsening-free in Months 6 to 18 (yes/no)
 
NEDA clinical in Months 6 to 18 (yes/no)
 
NEDA radiological in Months 6 to 18 (yes/no)
 
Change from baseline in conventional MRI metrics (Gd+ lesion number, new Gd+ lesion number, Gd+ lesion volume, T2 lesion number (Baseline), new/enlarging T2 lesion number (post-Baseline), T2 lesion volume, new/enlarging T2 lesion volume, new unenhancing T1 lesion number, T1 unenhancing lesion volume)
 
Change from baseline in PROs (NeuroQOLTM, PDDS) (also obtained in healthy controls)
 
Brain volume assessment (whole brain and regional) (also obtained in healthy controls)
 
Adverse events, laboratory data, physical examination, and vital signs (also obtained in healthy controls)
 

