### Change and percent change from baseline

Change from baseline will be calculated as follows:

- Post-baseline value – baseline value

Percent change from baseline will be calculated as follows:

- $[(\text{Post-baseline value} - \text{baseline value}) / \text{baseline value}] \times 100\%$

Change and percent change from baseline will only be calculated and summarized for participants with both baseline and post-baseline values.

Change and percent change from Month 6 re-baseline will be calculated in a similar fashion using the above formulas where ‘baseline value’ is replaced with ‘Month 6 re-baseline value’ (i.e., Month 6 value) and ‘Post-baseline value’ is replaced with ‘Post-Month 6 value’.

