## 2.6.2 Statistical hypothesis, model, and method of analysis

Values, changes from baseline and percent changes from baseline (brain volume parameters only) in the following endpoints will be summarized by Cohort and time point with descriptive statistics using the FAS or HCAS, as appropriate:

- Conventional MRI metrics including Gd+ lesion number, Gd+ lesion volume, T2 lesion volume and T1 unenhancing lesion volume
- Brain volume parameters (whole brain and regional)

In addition, changes and percent changes (for applicable endpoints) from Month 6 re-baseline to post-Month 6 time points will be summarized in a similar fashion.

Percent change from Month 6 re-baseline to post-Month 6 time points in brain volume parameters will be calculated via the following steps:

1. Calculate normalized brain volume (NBV) at post-baseline time points as follows (note that NBV at baseline and percentage brain volume change [PBVC] at post-baseline time points are provided by the MRI vendor):  
NBV at post-baseline time point = [(PBVC at post-baseline time point/100) x NBV at baseline] + (NBV at baseline)
2. Calculate the percent change from Month 6 re-baseline to post-Month 6 time points using the NBVs at Month 6 re-baseline and Months 12, 18 and 30 from Step 1 according to the formula provided in [Section 2.1.1](#).

Values of the following endpoints will be summarized by Cohort and time point (baseline or post-baseline, as appropriate) with descriptive statistics using the FAS or HCAS, as appropriate:

- Conventional MRI metrics including new Gd+ lesion number, T2 lesion number, new/enlarging T2 lesion number, new unenhancing T1 lesion number and new/enlarging T2 lesion volume

The annualized new/enlarging T2 lesion rate will be calculated using a participant-based approach and a cohort-based approach as follows:

- Participant-based approach: [(number of new/enlarging T2 lesions in Months 6 to 18 for a given participant) / (number of days in Months 6 to 18 for a given participant)] × 365.25
- Cohort-based approach: [(total number of new/enlarging T2 lesions in Months 6 to 18 for all participants within a cohort) / (total number of days in Months 6 to 18 for all participants within a cohort)] × 365.25

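### The Month 18 and Month 30 rows will rest on different participants, so comparing them cannot by itself show stability over the optional extension

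*SAP*

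**What the plan says.** **Who is measured at Month 30.** The extension is elective. Protocol section 3 discharges participants after the main treatment period "if they choose to not be included in the optional extension portion of the trial". Table 8-1 schedules consent again at Month 18 for ofatumumab participants and healthy controls, and footnote 13 limits it: "Only for participants continuing onto the 12-month open-label extension period".

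**What Month 30 is for.** SAP section 1.1 places further efficacy and safety assessment "during the optional open-label extension period to further elucidate the long-term clinical and radiological effects" of the drug. Protocol section 1.2 says that "the extension data of up to 30 months would potentially show stabilization long term". A secondary objective in SAP Table 1 compares ofatumumab with healthy controls on "whole brain and regional atrophy measured at Month 18/30 after re-baseline at 6 months".

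**How it is summarized.** SAP section 2.1 puts all data through Month 30 into the final analysis. Under SAP section 2.6.2, MRI volumes and brain volume "will be summarized by Cohort and time point with descriptive statistics using the FAS or HCAS, as appropriate", and brain-volume change is calculated "using the NBVs at Month 6 re-baseline and Months 12, 18 and 30". Section 2.10 treats NeuroQOL and PDDS in the same way. Change is defined from baseline or from Month 6, and under section 2.1.1 change from baseline "will only be calculated and summarized for participants with both baseline and post-baseline values". For these endpoints sections 2.6.3 to 2.6.6 plan no imputation and no sensitivity or supplementary analysis, and section 2.2.1 plans no subgroups. Section 2.13 states that nothing will be tested or estimated at Month 30.

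**The concern.** A claim of stabilization over the extension is a claim about Month 18 to Month 30. The plan defines no change over that interval for lesion volume, brain volume or patient-reported outcomes. A reader who wants to judge it will compare the Month 18 row with the Month 30 row, and the two rows contain different people.

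If those who continue differ at Month 18 from those who leave, the difference between rows mixes real change with a change in who is measured. It can err in either of two ways:

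- an apparent gain when no one has changed;
- a flat line when entrants have in fact worsened.

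The same applies in the healthy controls, with their own uptake and their own reasons for staying. At stake is the interpretation of the extension against its stated aim, not the primary result.

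**Working it through.** **The plan's own figures.** No figure is given for extension uptake or for Month 30. The only sample-size statement (SAP section 3.1) is 100 evaluable and 118 enrolled, with half-widths of 7.8% and 7.0%. It reproduces:

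- 1.96 × √(0.80 × 0.20 / 100) = 0.0784
- 1.96 × √(0.85 × 0.15 / 100) = 0.0700
- 100 / 0.85 = 117.6, rounded up to 118

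I use 100 as the number with Month 18 data.

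**Which rows are exposed.** These are T2 lesion volume, T1 unenhancing lesion volume, brain volume, NeuroQOL and PDDS. Gadolinium imaging is scheduled only at baseline and Months 6 and 18 (Protocol Table 2-1), so there is no scheduled Month 30 Gd+ row. NEDA-3, NEDA clinical, NEDA radiological and 3-month disability worsening-free are defined in Months 6 to 18, and relapse rates stop at Month 18.

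**Formula.** Let f be the share of participants with Month 18 data who also supply Month 30 data. Let μE and μN be the Month 18 means of entrants and non-entrants, and D = μE − μN.

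- Month 18 row: f·μE + (1 − f)·μN
- Month 30 row, if nobody changes: μE
- Difference between rows: (1 − f) × D

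**Values, in SD units. Both f and D are assumptions.**

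| f | D = 0 | D = 0.3 | D = 0.5 |
|---|---|---|---|
| 0.5 | 0 | 0.15 | 0.25 |
| 0.6 | 0 | 0.12 | 0.20 |
| 0.7 | 0 | 0.09 | 0.15 |
| 0.8 | 0 | 0.06 | 0.10 |
| 1.0 | 0 | 0 | 0 |

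The standard error of the Month 30 mean is 1/√(100f), which is 0.141 at f = 0.5 and 0.112 at f = 0.8. For f of 0.5 to 0.8 and D of 0.3 to 0.5, the shift therefore runs from 0.06/0.112 = 0.54 to 0.25/0.141 = 1.77 standard errors.

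**Example on the brain-volume scale (assumed values).** Take f = 0.7 and a Month 6 to 18 change of −0.3% in entrants and −0.7% in non-entrants.

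- Month 18 row: 0.7 × (−0.3) + 0.3 × (−0.7) = −0.42%
- Month 30 row if nobody changes: −0.30%, an apparent gain of 0.12 points
- Month 30 row if entrants lose a further 0.12 points: −0.42%, which looks stable

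At f = 0.5 the shift is 0.5 × 0.4 = 0.20 points; at f = 0.9 it is 0.1 × 0.4 = 0.04 points.

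**With the same participants at both time points.** Month 18 and Month 30 are then both averaged over entrants. If nobody changes, the difference is μE − μE = 0 for every f and D.

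**The case against.** The case against has several parts.

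- **The Month 30 rows are valid as they stand.** Each change is within-participant from baseline or Month 6 and correctly describes those measured. The plan does not subtract one row from another, and it disclaims testing and estimation at Month 30. This is right and limits the point to interpretation. But the change is within-participant only inside a row. Tabulating the rows together for a stated long-term aim invites the comparison.
- **The smaller group is visible.** The number with data is reported at each time point and extension disposition is summarized. That shows how many left, not whether they differed.
- **Selection is not shown.** A reader might infer that participants who do well are the ones who stay. The documents do not establish this. Staying requires ofatumumab monotherapy, which makes a link to outcome plausible. Yet completers can continue on commercial drug, so leaving need not mean poor response, and controls receive no treatment. Both the size and the direction of D are unknown.
- **One lesion outcome may already be covered.** SAP section 2.6.2 counts new or enlarging T2 lesions at Month 12 against Month 6, and at Month 18 against Month 12. The Month 30 reference scan is not stated. If the pattern continues, that count is already a Month 18 to Month 30 measure.
- **The table may exist out of sight.** Parts of the SAP are redacted and the TFL shells are not available. This cannot be excluded.

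**Conclusion.** The point holds in a limited form. In the readable plan, the Month 18 and Month 30 rows for T2 and T1 unenhancing lesion volume, brain volume and patient-reported outcomes rest on different participants, and nothing puts the two time points on the same ones. If continuation is related to outcome, the row-to-row difference is off by (1 − f) × D: 0.06 to 0.25 SD over the assumed range, and zero with complete or outcome-independent uptake.

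Three stronger readings are tempting and are not supported:

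- That the tables could show a false stabilization when nobody changes. If nobody changes, stability is true. The errors are false improvement, or stability that hides worsening.
- That Month 18 represents everyone enrolled. It covers only those with Month 18 data, so early discontinuers without a value are already absent.
- That the main efficacy conclusions are affected. NEDA-3 and the other Months 6 to 18 endpoints have no Month 30 row.

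This is an inexpensive improvement to a descriptive analysis, worth making because the extension cannot otherwise answer the question set for it.

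**What to change.** In SAP sections 2.6.2 and 2.10, for the final analysis:

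1. For participants with both values, present Month 18, Month 30 and the within-participant Month 18 to Month 30 change, by cohort, as descriptive statistics. If a 95% CI is added, reconcile it with the statement in SAP section 2.13 that there is no estimation at Month 30.
2. Present Month 18 status for extension entrants versus non-entrants: brain-volume change from Month 6, lesion volumes and patient-reported outcomes in both cohorts, and NEDA-3 in ofatumumab participants only.
3. State that any description of stability from Month 18 to Month 30 rests on item 1, not on comparing the time-point rows.

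If the TFL shells already contain these tables, a cross-reference in the SAP is enough.

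The cost is SAP wording and a few descriptive tables from data already collected. The limitation is that item 1 describes extension entrants only; item 2 lets a reader judge how far they resemble the rest.
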